13.6 Exploratory Objectives

The effect of perampanel on neurocognition and patient-reported outcomes of quality of life will be explored. Mean changes from baseline in neurocognition and QOL subscales will be computed at each follow-up assessment.

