6 OBJECTIVES AND ENDPOINTS

	Objective	Endpoint	Analysis
Primary	To determine the efficacy of perampanel as an adjunctive AED in patients with primary glioma presenting refractory partial onset seizure activity	Percentage of patients with ≥50% seizure reduction during the treatment period compared with seizure frequency before initiation of perampanel (i.e. 50% responder rate)	See Section 13.4
Secondary	To assess the safety and tolerability of perampanel as an adjunctive AED in patients with primary glioma presenting with refractory partial onset seizure activity	The percentage of patients who experience a adverse event possibly, probably, or definitely attributable to perampanel treatment	See Section 13.5
Exploratory	To evaluate the effect that perampanel has on neurocognition and patient-reported outcomes of quality of life (QoL) in patients with primary glioma presenting with refractory partial onset seizure activity	Mean change from baseline for each neurocognitive and QoL subscale score at each follow-up assessment	See Section 13.6

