Perampanel will be given according to FDA-approved guidelines over a 24-week period. Patients will be started on a dose of 2 mg daily taken orally at bedtime for 2 weeks. At the start of week 3 Perampanel will be titrated up in dose in 2mg increments per week up to 8mg daily, as long as it is well tolerated by the patient. Weeks 1 and 2, patients will take 2mg, Week 3 they will take 4 mg, Week 4 they will take 6mg and starting at week 5 they will take 8mg. Highest dose will be 8 mg orally at bedtime. Starting at week 5, patients will begin the treatment period, which goes from day 1 of Week 5 through day 7 of Week 16. Patients will be assessed in the Brain Tumor Center Clinic every 8 weeks. Assessments will be made at enrollment, 8 weeks, 16 weeks, and 24 weeks. Assessments will include history, physical examination, neurological examination, evaluation of seizure history, patient-reported outcomes of quality of life, and neurocognitive testing using CNS Vital Signs®. After a total of 16 weeks on therapy, perampanel will be tapered down. At Week 17, patients will begin taking 6mg of perampanel, Week 18 4mg, Week 19 2mg, and Week 20 they will no longer take perampanel. Patients will be considered off treatment at the end of week 20, once perampanel has cleared their system. The planned treatment dose is 8mg, but the dose can be modified by the physician based on patient reported tolerability. Titration and taper periods will be determined by the physician in the case where patients do not reach the planned treatment dose of 8 mg daily. Patients will continue to take their original AED regimen after they stop perampanel. Patients will then be monitored through Week 24. Patients will remain on their original AED regimen during this treatment time and the dose of their original AED at the start of the study will not be changed while they are on study. If seizure control is achieved during the treatment period or if seizures occur during the tapering period, patients can be continued on perampanel per the discretion of the treating physician. In this instance, perampanel will be prescribed by the treating physician and not provided within the confines of the study. As is standard procedure at the PRTBTC, patients will be given a log to record the number of seizures that occur. Research team members will regularly contact patients for reminders and reports from the log.

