10.7.3 Replacement of Early Withdrawal(s)

Not applicable.

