13.1 Analysis Sets

As indicated in section 7.4, subject to the availability of data, all patients who receive perampanel treatment will be included in safety analyses. All patients who complete the treatment period of the study will be included in efficacy analyses.

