13.8 Sample Size Calculation

The one-arm study will assess the efficacy of perampanel for the treatment of primary brain tumor patients with partial onset seizures. The basis for this assessment is the percentage of patients with a $\geq 50\%$ seizure reduction during the treatment period compared with the seizure frequency before initiation of perampanel (i.e. 50% responder rate).

Several recently conducted randomized studies of patients with partial-onset seizures have reported a 50% responder rate of approximately 20% within the standard treatment arm.²⁻⁴ Steinhoff (2009) also reports a 50% responder rate of approximately 35% within a general population of patients with partial-onset seizures treated with perampanel.²

This study has been designed with 90% power to detect an increase in the 50% responder rate during the treatment period from a benchmark of 20% to 35%. Assuming a type I error rate of 0.1, 61 patients will be required. Based on prior studies the early discontinuation rate was 16%, therefore 71 patients will be enrolled to compensate for patients discontinuing prior to the completion of the treatment period.

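### Neurocognition and QoL are summarised only as visit-by-visit mean changes with no rule for missing scores; if declining patients leave, the later means shift toward no harm

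*Combined protocol and SAP*

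**What the plan says.** The endpoint table in Section 6 defines the exploratory endpoint as "Mean change from baseline for each neurocognitive and QoL subscale score at each follow-up assessment". Section 13.6 gives the method in one sentence: "Mean changes from baseline in neurocognition and QOL subscales will be computed at each follow-up assessment". The schedule in Section 7.1 is "Assessments will be made at enrollment, 8 weeks, 16 weeks, and 24 weeks".

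Section 13.1 names two analysis sets. For safety, "subject to the availability of data, all patients who receive perampanel treatment will be included in safety analyses". For efficacy, "All patients who complete the treatment period of the study will be included in efficacy analyses". Neither is assigned to neurocognition or QoL.

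On attrition, Section 13.8 states "Based on prior studies the early discontinuation rate was 16%, therefore 71 patients will be enrolled". Replacement of withdrawals (Section 10.7.3) is "Not applicable". Reasons for withdrawal in Section 10.7.1 include intolerable symptoms and coming to meet an exclusion criterion. One exclusion criterion in Section 3.3 is being unable to complete the patient-reported measures or the computerised testing.

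Leavers are asked for an exit assessment, but it is described in two ways. Section 10.4 asks anyone withdrawing early for the End of Treatment procedures. Section 10.7.2 asks voluntary withdrawers for the procedures of their next scheduled visit. Under Section 10.3 both include QoL and neurocognitive testing. Neither section says to which visit the exit score belongs, or whether it enters the visit means.

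**The concern.** A mean over patients with a score at a given visit estimates the mean for all treated patients only if those without a score changed, on average, as the others did. The protocol's own rules give a reason to doubt this. A patient whose cognition falls far enough to prevent testing may be withdrawn, and so may a patient who tolerates the drug badly. Such patients would be missing from the later means that are meant to describe cognition and QoL.

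There is no control arm, so a shift of this kind cannot cancel in a between-arm contrast. For the BDI-II, where a higher score is worse, it would appear as too small a rise. What is at stake is how the Week 8, 16 and 24 means can be read: partly as change over time, partly as change in who is being averaged.

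**Working it through.** **The plan's own figures.** No figure is stated for the exploratory analysis. The sample size behind the 16% does reproduce. An exact one-sided binomial test of 20% against 35% with 61 patients and success at 17 or more responders has type I error 0.0879 and power 0.9055. Then 61 × 1.16 = 70.8, which gives 71. Nothing below depends on the test itself.

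**Inputs from the documents.** 71 enrolled; share leaving d = 0.16 by the end of the treatment period (no figure is given through Week 24); visits at Weeks 8, 16 and 24.

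**Assumed inputs.** The documents give no SD, correlation, true decline or dropout mechanism. I take change scores with SD 1, true mean change -0.10 at Week 8 and -0.20 at Week 16, correlation ρ of 0.5 or 0.7 between them, and a log-odds of leaving after Week 8 that rises by a fixed amount per SD of Week 8 decline. Leavers are taken to have no Week 16 score.

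**Precision.** 71 × 0.84 = 59.6 remain, so the standard error of a mean change is 1/√59.6 = 0.129 SD.

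**Formula.** Shift = d × Δ, where Δ is the mean Week 16 change of stayers minus that of leavers. When leaving depends only on the Week 8 change, Δ = ρ × Δ8, with Δ8 the same difference at Week 8. Δ8 comes from simulation with the dropout rate set to 16%.

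| Log-odds per SD | Δ8 | Shift, ρ = 0.5 | Shift, ρ = 0.7 | Raw Week 16 mean (true -0.20) |
|---|---|---|---|---|
| 0 | 0 | 0 | 0 | -0.20 |
| 0.3 | 0.30 | 0.16 × 0.5 × 0.30 = 0.024 | 0.034 | -0.18 to -0.17 |
| 0.5 | 0.48 | 0.038 | 0.054 | -0.16 to -0.15 |
| 1.0 | 0.88 | 0.070 | 0.099 | -0.13 to -0.10 |
| 1.5 | 1.16 | 0.093 | 0.130 | -0.11 to -0.07 |

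At log-odds up to 0.5 the shift is below half a standard error (0.054/0.129 = 0.42). At 1.5 it is 0.7 to 1.0 standard errors. If 25% left instead, log-odds of 1.5 would give raw means of -0.06 (ρ = 0.5) and -0.01 (ρ = 0.7).

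**What a model recovers.** Regressing Week 16 on Week 8 change and predicting for leavers returns -0.20 in every row of the table. That follows from the set-up: leaving depends only on an observed score, and every leaver has that score. If leaving depends instead on the unseen Week 16 change, the same estimate at 16% leaving and log-odds 0.5 to 1.5 is -0.14 to -0.06 (ρ = 0.5) or -0.16 to -0.10 (ρ = 0.7), against raw means of -0.12 to -0.01. The model is closer to the truth than the raw mean but does not reach it.

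**The case against.** - **The missing-score reading is inferred.** Section 13.6 does not say that the means cover only those still attending. That stands, but the section offers no other method, and leavers without a later score would be absent under either set in Section 13.1.
- **The size is assumed.** This also stands. A reader might infer that half or more of any decline would be lost. That describes only log-odds near 1.5 per SD, where leavers are already 1.16 SD worse than stayers at Week 8. The documents do not support choosing that case over a weak or null one.
- **Exit assessments are requested.** The plan asks leavers for a score near the time of leaving, which the table above ignores. This is a real mitigation, but a partial one: the use of that score is unspecified and later visits stay missing.
- **The direction is not certain.** Section 7.1 lets patients whose seizures are controlled continue perampanel by ordinary prescription. If they stopped study assessments, the missing patients could be those doing well.
- **The consequence is limited.** The objective is exploratory, with no test, threshold or planned claim of no harm. Adverse events are recorded from the first dose (Section 11.1), and suicidal ideation of any grade counts as unacceptable in Section 13.5. A reader might infer that worsening mood would go unseen; these provisions argue against that, though they do not replace the cognitive and QoL scores. Without a control arm, even unbiased means cannot separate drug from tumour or chemotherapy.

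**Conclusion.** The point holds as a conditional statement. The plan leaves missing neurocognitive and QoL scores unaddressed, while its withdrawal rules allow missingness to be tied to decline. If leavers are declining, later means shift toward no harm. Under the assumptions above, with 16% leaving, the shift runs from 0, through 0.02 to 0.06 SD at log-odds 0.3 to 0.5, to 0.09 to 0.13 SD at log-odds 1.5, against a standard error of about 0.13 SD.

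Two stronger readings are not supported. The documents do not show that the later groups will be healthier or that decline will be hidden, because they give no dropout mechanism and the direction could reverse. Nor can a repeated-measures model be said to remove the bias: it does so only when leaving depends on observed scores, and it cannot use patients who leave during titration with no post-baseline score.

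The matter is minor. It concerns an exploratory objective and leaves the primary conclusion unaffected. It is worth correcting because the better analysis uses data the plan already asks for.

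**What to change.** In Section 13.6:

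- Analyse change from baseline with a likelihood-based repeated-measures model (visit as factor, baseline score as covariate, unstructured covariance), using all post-baseline scores including exit assessments.
- Reconcile the exit-assessment wording of Sections 10.4 and 10.7.2, and state to which visit an exit score is assigned.
- Report adjusted mean changes with 95% intervals, and keep the raw means beside them.
- At each visit, show the number assessed, the number expected, and the last observed change of those who left.
- Report separately the patients with no post-baseline score.
- Label Week 24 as off-drug after the planned taper, so that its mean is not read as an on-treatment result.

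The cost is a few lines of text and some code, with no new data. The downside is the assumption that leaving depends on observed scores. Where leaving follows unobserved decline the correction is only partial, so the results should stay descriptive.

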3.4 Risk/Benefit Assessment

The full prescribing information for Perampanel (FYCOMPA™) includes the following boxed warning¹:

WARNING: SERIOUS PSYCHIATRIC AND BEHAVIORAL REACTIONS

- Serious or life-threatening psychiatric and behavioral adverse reactions including aggression, hostility, irritability, anger, and homicidal ideation and threats have been reported in patients taking FYCOMPA
- These reactions occurred in patients with and without prior psychiatric history, prior aggressive behavior, or concomitant use of medications associated with hostility and aggression
- Advise patients and caregivers to contact a healthcare provider immediately if any of these reactions or changes in mood, behavior, or personality that are not typical for the patient are observed while taking FYCOMPA or after discontinuing FYCOMPA
- Closely monitor patients particularly during the titration period and at higher doses
- FYCOMPA should be reduced if these symptoms occur and should be discontinued immediately if symptoms are severe or are worsening

The most common adverse reactions that are associated with perampanel occurring in 10% of patients or greater are dizziness (36%), somnolence (16%), and fatigue (10%). Less common reactions are irritability (9%), falls (7%), nausea (7%), ataxia (5%), balance disorder (4%), gait disturbance (4%), vertigo (4%), and weight gain (4%).

With concomitant use, perampanel, at a dose of 12 mg/day, reduced levonorgestrel exposure by approximately 40%. Use of perampanel with oral or implant contraceptives containing levonorgestrel may render them less effective. Therefore, additional non-hormonal forms of contraception are recommended (please see the FYCOMPA FDA-approved labeling dated 6/11/2013).¹

The concomitant use of known CYP enzyme inducers including carbamazepine, phenytoin, or oxcarbazepine with perampanel decreased the plasma levels of perampanel by approximately 50~67%. The starting doses for perampanel should be increased in the presence of enzyme-inducing AEDs.¹ When these enzyme-inducing

AEDs are introduced or withdrawn from a patient's treatment regimen, patient should be closely monitored for clinical response and tolerability. Dose adjustment of perampanel may be necessary. As noted, however, the decrease in the therapeutic effect seen in patients on concomitant treatment, was not affected by use of higher doses (8 mg to 12 mg).¹

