7.3 Rationale for Correlative Studies

In order to capture fully the many aspects of QOL, we will utilize multiple questionnaires to evaluate issues of fatigue, cognition, and mood. The Functional Assessment of Cancer Therapy-Brain (FACT-Br) has been used extensively and has been documented to identify key QOL problems for brain tumor patients.¹⁶ Other standardized questionnaires will include Functional Assessment of Cancer Therapy-Fatigue, Functional Assessment of Cancer Therapy-Cognition, and Beck Depression Inventory. Additionally, neurocognition will be measured using computer-based models known as CNS Vital Signs®. These measurements have been validated and are being used extensively in our research in not only brain tumor patients, but also in patients with other forms of cancer.¹⁷

Quality of Life will be assessed by the Functional Assessment of Cancer Therapy-Brain (FACT-BR) scale. The FACT-BR (version 4) contains subscales for physical (7-items), functional (7-items), emotional (6-items), and social/family (7-items) well-being. In addition, this instrument contains an 23-item brain cancer subscale (BCS) which assess symptoms commonly reported by brain cancer patients.¹⁶ Cancer-related fatigue will be

assessed by the 13-item Fatigue Scale using the Functional Assessment of Cancer Therapy-Fatigue (FACT-Fatigue) subscale, version 4.¹⁸ Cognitive problems will be assessed using version 3 of the Functional Assessment of Cancer Therapy-Cognition (FACT-Cog) subscale.¹⁹ This includes subscales for perceived cognitive impairments (20 items), comments from others (4 items), perceived cognitive abilities (9 items), and impact of quality of life (4 items). Beck depression inventory (BDI) will be used to evaluate for underlying depressive symptoms. We will use the revised version (BDI-II) and the scores will range from 0 (no depression) to 63 (severe depression).²⁰ The BDI contains 21 questions in regards to mood symptoms and is multiple-choice and self-reported.

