10.8.4 Quality of Life and Neurocognitive Assessments

Patient-reported Quality of Life (QoL) outcomes will be assessed using the following standardized and validated questionnaires.

- Functional Assessment of Cancer Therapy-Brain (FACT-BR) scale (version 4), which contains subscales for physical (7-items), functional (7-items), emotional (6-items), and social/family (7-items) well-being, as well as a 23-item brain cancer subscale (BCS) that assesses symptoms commonly reported by brain cancer patients¹⁶
- Functional Assessment of Cancer Therapy-Fatigue (FACT-Fatigue) subscale, version 4¹⁸
- Functional Assessment of Cancer Therapy-Cognition (FACT-Cog) subscale, version 3, which includes subscales for perceived cognitive abilities (9 items) and impact on quality of life (4 items)¹⁹
- Beck depression inventory (BDI), revised version (BDI-II), which contains 21 questions regarding mood symptoms (multiple choice and self-reported). Scores range from 0 (no depression) to 63 (severe depression).²⁰

Neurocognitive testing will include the performance on the following testing using a computerized battery CNS Vital Signs®.²¹ This battery consists of seven tests that measure verbal and visual memory, finger tapping, symbol digit coding, the Stroop Test, a test of shifting attention, continuous performance test. Verbal memory test will assess verbal learning, memory for words, immediate recall, and delayed recall. Visual memory tests will assess visual learning, memory for geometric shapes, immediate recall, and delayed recall. Finger tapping test will assess motor speed and fine motor control. Symbol digit coding test will evaluate complex attention, visual-perceptual speed, and information processing speed. Stroop Test will assess executive function, simple and choice reaction time, speed-accuracy trade-off, information processing speed, and inhibition/disinhibition. Shifting attention test will assess executive function, reaction time, and information processing speed. Continuous performance test will assess sustained attention and choice reaction time. Normative data is available for this testing through CNS Vital Signs® and patients' performance will be compared to this normative data.

Patient demographics, disease history, and concomitant medications will be obtained for all study participants.

References for these standardized tests are provided in Section 15.

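### The depression inventory is summarised only as a mean change, which can sit near zero while a minority of patients worsen markedly

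*Combined protocol and SAP*

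**What the plan says.** Section 10.8.4 introduces its list of instruments with "Patient-reported Quality of Life (QoL) outcomes will be assessed using the following standardized and validated questionnaires". The BDI-II is on that list, as a scale "which contains 21 questions regarding mood symptoms (multiple choice and self-reported"). Of its total it says: "Scores range from 0 (no depression) to 63 (severe depression"). Section 7.3 gives its purpose as looking for depressive symptoms. Table 1 in Section 10 schedules the quality-of-life questionnaires at baseline and at 8, 16 and 24 weeks after the start of study drug.

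Two places state the analysis. The endpoint table in Section 6 has "Mean change from baseline for each neurocognitive and QoL subscale score at each follow-up assessment". Section 13.6 has "Mean changes from baseline in neurocognition and QOL subscales will be computed at each follow-up assessment". Neither gives a standard deviation, percentile, severity category, worsening threshold or worst value. Both refer to subscales, and the BDI-II is described by a single total. If the wording were read as leaving that total out, the scale would have no planned analysis at all.

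The nearest other scheduled measure is in the FACT-Br, which "contains subscales for physical (7-items), functional (7-items), emotional (6-items), and social/family (7-items) well-being". It is presented as quality of life and also receives only a mean change.

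Section 3.4 reproduces the label's boxed text, headed "WARNING: SERIOUS PSYCHIATRIC AND BEHAVIORAL REACTIONS".

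**The concern.** Marked worsening of mood in some patients is a question about individuals: how many, and by how much. A mean change answers a different question, namely the average shift across everyone. If most patients feel slightly better, for example because their seizures improve, and a few become much worse, the two movements offset each other and the mean shows neither.

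The plan handles other variables less narrowly. Section 13.4.2 describes the distribution across patients of the percent reduction in seizures, with quartiles if the data call for them. Section 13.2 allows medians and percentiles for baseline variables. The mood score has no such provision.

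At stake is the description of tolerability. The trial will hold up to four BDI-II scores per patient and could report them as unchanged although several patients moved a long way up the scale.

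**Working it through.** **The plan's own figure.** The plan gives no numbers for the BDI-II, so its sample size serves only as a denominator. An exact one-sample binomial test at one-sided 0.1, with 20% against 35% and n = 61, rejects at 17 or more responders. Its true type I error is 0.0879 and its power 0.9055. The stated 61 (Sections 3.5 and 13.8) is reproduced and not disputed. The planned enrolment of 71 is the other denominator used below.

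**Assumed inputs.** The documents give no BDI-II standard deviation, cut-off or rate of worsening. Assume k of N patients worsen by d points, with d = 15, 20 or 25 on the 0 to 63 scale.

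**Formulas.** If the other patients do not change, the mean change is k × d / N. The improvement in each of the others that makes the mean exactly zero is k × d / (N − k).

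| N | k (%) | d | Mean if others unchanged | Gain in others for mean zero |
|---|---|---|---|---|
| 61 | 3 (4.9%) | 15 | +0.74 | 0.78 |
| 61 | 3 (4.9%) | 20 | +0.98 | 1.03 |
| 61 | 3 (4.9%) | 25 | +1.23 | 1.29 |
| 61 | 6 (9.8%) | 15 | +1.48 | 1.64 |
| 61 | 6 (9.8%) | 20 | +1.97 | 2.18 |
| 61 | 6 (9.8%) | 25 | +2.46 | 2.73 |
| 71 | 7 (9.9%) | 15 | +1.48 | 1.64 |
| 71 | 7 (9.9%) | 20 | +1.97 | 2.19 |
| 71 | 7 (9.9%) | 25 | +2.46 | 2.73 |

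Worked row: 6 × 20 / 61 = 1.97, and 6 × 20 / 55 = 2.18.

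**Would an interval around the mean help?** None is planned, but suppose one were added to the worked case. The two groups differ by 20 + 2.18 = 22.18 points, which contributes a variance of (6/61)(55/61) × 22.18² = 43.6. With an assumed within-group SD of 0, 6 or 10, the total SD is √(s² + 43.6) = 6.6, 8.9 or 12.0. The 95% half-width, 1.96 × SD / √61, is then 1.7, 2.2 or 3.0. The result would be zero plus or minus 2 to 3 points, which still does not show the six patients.

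**What a patient-level summary would show.** Exact (Clopper-Pearson) 95% intervals:
- 3/61 = 4.9% (1.0% to 13.7%)
- 6/61 = 9.8% (3.7% to 20.2%)
- 7/71 = 9.9% (4.1% to 19.3%)
- 0/61 = 0% (upper limit 5.9%)

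The zero case is also informative, since it bounds the proportion that worsened, which a mean near zero cannot do.

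**The case against.** The strongest reply is that psychiatric harm is already counted per patient through adverse events. Section 6 makes the percentage of patients with any attributable event the secondary endpoint. Section 13.5 counts related Grade 4 or 5 toxicities, suicidal ideation of any grade, and suicide attempt. Section 11.1 records every event from the first dose, including worsening of existing conditions. Section 11 lets study assessments as well as questioning reveal an event, so a sharply worse BDI-II could lead to one being recorded. This largely stands: reporting of psychiatric harm does not rest on the BDI-II mean. But no rule turns a rise in score into an event. Depression of Grade 3 or lower without suicidal ideation falls outside the Section 13.5 count, and in the Section 6 endpoint it is merged with every other attributable event.

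A second reply is that the objective is exploratory, that mean change is a conventional summary for it, and that the illustration uses values chosen to cancel. That is fair as to weight. The values are assumptions. They show what the summary can hide, not what is likely to happen.

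A reader might go further and infer that the known harm of this drug will be misreported from data that show it. The documents do not support that. The boxed text says "Serious or life-threatening psychiatric and behavioral adverse reactions including aggression, hostility, irritability, anger, and homicidal ideation and threats have been reported", whereas the BDI-II is described as a measure of depressive symptoms. The rates a reader might borrow, 9% in Section 3.4 and 6.7% at 8 mg in Section 5.2.2, are for irritability. The second has a placebo rate of 2.9% beside it, an excess of 3.8 percentage points. No rate of depression or of BDI-II worsening on perampanel is given.

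**Conclusion.** The point holds as a gap in an exploratory summary. The one dedicated depression scale has a planned analysis that cannot reveal a minority with large worsening. Under the assumed values, about 10% of patients worsening by 15 to 25 points moves the mean by only 1.5 to 2.5 points of 63, and a gain of 1.6 to 2.7 points in the others removes even that. The direction needs only arithmetic. The size rests on assumptions, because the documents give no distribution for the score.

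The consequence is limited to the description of tolerability. The primary test and the adverse-event endpoint are untouched, and the scale reaches only the depressive part of the psychiatric risk. This is a low-cost improvement, not a flaw that threatens the trial.

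**What to change.** Keep the mean change in Section 13.6 and add the following, for all treated patients with a baseline and at least one later BDI-II:

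- The median, quartiles and maximum of the change at each visit.
- The number and percentage of patients whose worst on-drug score worsens by a stated number of points or moves to a higher severity category, with an exact 95% CI. On-drug scores are those at Weeks 8 and 16, or at an early-withdrawal visit if the patient is still taking perampanel. The documents contain no cut-off, so the investigators must fix it before analysis.
- A table of baseline category against worst on-drug category.
- Week 24 shown separately as off study drug. Section 7.1 has study perampanel stopped at Week 20, so pooling Week 24 into a worst value would mix on-drug and off-drug scores. Patients continued on prescribed perampanel, which the same section allows, should be identified.

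Label the result descriptive. There is no control arm, tumour and chemotherapy also affect mood, and the worst of several visits picks up some random fluctuation.

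The cost is a paragraph of analysis wording and two small tables from scores already collected. It adds no visit or instrument and sets no clinical rule.
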